## 1. SUMMARY OF THE STUDY

TITLE	Retrospective Observational Cohort Study SYMBOL CUP 2
SHORT TITLE	SYMCOR-2
INVESTIGATOR	[name] [name]
SPONSOR	DEDIENNE SANTE S.A.S.
JUSTIFICATION / CONTEXT	Documentation of the clinical efficacy and safety of SYMBOL CUP DMR HA and SYMBOL CUP DM CEM dual mobility acetabular implants.
METHODOLOGY	Retrospective observational cohort study
MAIN OBJECTIVE	Estimate the safety of these implants under normal conditions of use
PRIMARY ENDPOINT	Implant survival rate at 2-year follow-up
SECONDARY OBJECTIVE	Estimate the efficacy of these implants under normal conditions of use
SECONDARY ENDPOINTS	
 
- Safety: Intra and extra-prosthetic dislocation rates
 
- Safety: Incidence of other adverse events
 
- Effectiveness: Harris Hip Score (HHS)
 
- Effectiveness: Devane classification
 
- Effectiveness: Charnley classification
 

INCLUSION CRITERIA	
 
- Any patient operated by [name] who has undergone hip replacement surgery with SYMBOL CUP DMR HA or SYMBOL CUP CEM acetabular implant.
 
- Patient having reach 2-year follow-up on March 01, 2018
 

NON-INCLUSION CRITERIA	
 
- Explicit refusal by the patient to allow data describing his pathology and treatment to be included in this study.
 
- Minor patients or patients under guardianship.
 

RESEARCH PROCESS	
Retrospective collection of clinical data:
 
 
- Recorded in the orthopedic surgery department's patient files, from the patient's pre-surgical assessment to the latest news at 2-year follow-up.
 
- Obtained by telephone interview for data up to 2-year follow-up, if the medical file does not provide all the source information. The telephone interview will be carried out by the investigator (or his secretariat) or by a clinical research associate delegated by the sponsor and approved by the investigator.
 

NUMBER OF SUBJECTS	Minimum total number of subjects: n=20
PLANNED NUMBER OF CENTERS	Single-center, single-investigator study
PROVISIONAL STUDY TIMETABLE	
CPP notice: N.A.  CEREEs notice: N.A.  CNIL receipt: 2176595  Start of the study: As soon as CNIL receipt is received.  Duration of inclusion period/data collection: N.A. given retrospective nature  Duration of participation of each subject: N.A. given retrospective nature  Anticipated end of study: N.A. given retrospective nature  End-of-study report: Within 30 days of start of study

STATISTICAL DATA ANALYSIS	
 
- Descriptive statistics: preoperative, operative, postoperative
 
- Tabulation of adverse events
 
- Kaplan-Meier analysis of implant survival
 
- Comparison tests of preoperative versus 1-year and 2-year postoperative efficacy scores.
 

## 2. STUDY RATIONALE / SCIENTIFIC JUSTIFICATION

### 2.1. CURRENT KNOWLEDGE OF THE PATHOLOGY

Hip replacement is the last therapeutic resort for symptomatic coxopathies, the incidence of which is estimated at over 85,000 patients per year, if hip replacement is considered as an indicator of this

pathology, according to data from the Programme de Médicalisation des Systèmes d'Information (PMSI).

In the report of 2014, the Haute Autorité de Santéi, recommends the use of dual-mobility acetabular implants:

- In first-line arthroplasties in patients with a very high risk of dislocation (severe neurological impairment, neuropsychiatric disorders, addiction, and major neuromuscular failures),
- And revision arthroplasties in case of iterative dislocation and in patients at high risk of dislocation,
- Depending on the clinical situation, press-fit fixation is the preferred method of fixation for the metal-back dual mobility acetabular cups, when the bone bed is of good quality.

In current practice, dual-mobility acetabular implants with cemented fixation in a cross shell, or with cortical screws and peg, are chosen when damage to the bed bone is extensive and does not allow direct press-fit implantation. This is particularly the case in revision surgery.

SYMBOL CUP DMR HA acetabular implants comprise metal-back cup with cortical screw fixation and peg fixation and the same DUAL MOBILITY PE LINER dual-mobility polyethylene insert as in all acetabular implants in the SYMBOL CUP DM range (Table 1, Figure 1).

**Table 1 : SYMBOL CUP DMR HA with cortical screw and pegs: technical specifications**

	RANGE (Manufacturer)	SYMBOL CUP DMR HA (Dediennne Santé)	Also sold under the brand names: GYRACUP Ultimate (AESCLAP), DS Evolution (MATHYS Ltd.)	
Cups	Model	Symbol Cup DMR HA		
	Diameter range	44 to 68mm		
	Metal-back material	Co-Cr (ISO 5832-4)		
	Coating	Ti +HAP (ISO 13779-2)		
	Fixation	* Press-Fit + Tripod	* 2 pegs through holes in cups	* 1 cortical screw in the flange
Liners	Model	Dual Mobility PE Liner		
	Material	polyethylene ISO 5834-2 UHMWPE		
	Diameter range	44 to 68mm		
	Range of diameters for corresponding femoral heads	22,2mm or 28mm		

**Figure 1 Photos of SYMBOL CUP DMR HA and PE LINER medical devices.**

SYMBOL CUP DM CEM acetabular implants comprise a metal-back cup designed to be cemented to the surrounding bone, and the same DUAL MOBILITY PE LINER dual-mobility polyethylene insert as in all acetabular implants in the SYMBOL CUP DM range (Table 2, Figure 2).

**Table 2 : SYMBOL CUP DM CEM to be cemented: technical specifications.**

	RANGE (Manufacturer)	SYMBOL CUP DM CEM (Dedienne Santé)	Also sold under the brand names: GYRACUP E (AESCULAP), DS Evolution (MATHYS Ltd.)
Cups	Model	Symbol Cup DM CEM	
	Diameter range	44 to 68mm	
	Metal-back material	Co-Cr (ISO 5832-4)	
	Coating	N.A	
	Fixation	Cement	
Liners	Model	Dual Mobility PE Liner	
	Material	Polyethylene ISO 5834-2 UHMWPE	
	Diameter range	44 to 68 mm	
	Range of diameters for corresponding femoral heads	22,2mm or 28mm	

**Figure 2 Photos of SYMBOL CUP DM CEM and PE LINER medical devices.**

## **2.2. STATE OF KNOWLEDGE ON THE DEVICES UNDER EVALUATION**

SYMBOL CUP DMR HA and SYMBOL CUP DM CEM are class III implantable devices according to rule N°20 of the decree of April 20, 2006, laying down the rules for the classification of medical devices (transposition of Annex IX of directive 93/42/EEC and Directive 2005/50/EC).

These implants have been introduced on the market in France and elsewhere in Europe since the EC declaration of conformity of April 09, 2014ii. Conformity is based in particular on:

- Certificate N°27262 of device design examination according to Annex II section 4 of Directive 93/42/EEC issued by the Notified Body LNE/G-MED N°0459, updated by revision 5 dated September 01, 2015.iii
- The clinical evaluation « Cotyles de hanche, double mobilité, SYMBOL CUP DM » dated 28/11/2013 performed by Dedienne Santé, updated on 28/11/2014.iv
- And the validation of the clinical evaluation report by the Notified Body LNE/G-MED.v

The clinical evaluation of SYMBOL CUP DMR HA and SYMBOL CUP DM CEM as part of CE conformity is based on a literature review of equivalent products, with no data specific to these products. Nevertheless, the CE mark has authorized SYMBOL CUP DMR HA to be reimbursed by the French health insurance, under the Liste des Produits et Prestations Remboursables, under generic code 3168042 (reconstruction cup, modular, metal-back, without insert, uncemented) and SYMBOL CUP DM CEM under generic code 3150450 (standard cup, modular, metal-back, without insert, cemented). In both cases, the insert was covered under generic code 3161130 (solid polymer insert). The patients identified for this retrospective study benefited from reimbursement of the implant according to these generic codes.

Given the relatively recent market introduction of SYMBOL CUP DMR HA and SYMBOL CUP DM CEM, a patient cohort with a minimum 2-year follow-up, 2-year follow-up data and sufficient numbers was only reached in 2018. The retrospective study proposed here is therefore the first clinical evaluation specific to these products.

The number of units of SYMBOL CUP DMR HA and SYMBOL CUP DM CEM fitted in France are summarized in Table 3 and Table 4 respectively.

**Table 3 : SYMBOL CUP DMR HA: Sales volume in France under this brand**

Year	2014	2015	2016	2017	Provisional 2018
In public healthcare facilities	0	0	4	8	16
In non PHSPH private healthcare facilities	15	194	98	128	155
Total	15	194	102	136	171

**Table 4 : SYMBOL CUP DM CEM: Sales volume in France under this brand**

Year	2014	2015	2016	2017	Provisional 2018
In public healthcare facilities	0	0	0	20	50
In non PHSPH private healthcare facilities	19	172	76	180	360
Total	19	172	76	200	410

The specific data resulting from this study will be used to establish the benefit-risk ratio of SYMBOL CUP DMR HA and SYMBOL CUP DM CEM. This information will enable:

- Update of the clinical evaluation for CE mark renewal purposes.
- An assessment of the product's application for inclusion in the Liste des Produits et Prestation Remboursables under the brand names by the Haute Autorité de Santé.

### **2.3. STUDY HYPOTHESES AND EXPECTED RESULTS**

The aim of this observational study is to estimate the risk and benefit of this implant in current clinical practice. As the approach is descriptive, no hypotheses have been made concerning the incidence of adverse events, or variations in endpoints during follow-up.

## **3. STUDY OBJECTIVES AND ENDPOINTS**

### **3.1. MAIN OBJECTIVE**

Estimate the safety of these implants under normal conditions of use.

### **3.2. PRIMARY ENDPOINT**

Implant survival rate at 2-year follow-up. This is the probability over time that the implant will remain in place in the living patient's hip. Events that reduce this probability are revision surgeries with removal of the implant, for whatever reason.

### **3.3. SECONDARY OBJECTIVE**

Estimate the efficacy of these implants under normal conditions of use.

### **3.4. SECONDARY ENDPOINTS**

- Safety: Intra and extra-prosthetic dislocation rates
- Safety: Incidence of other adverse events
- Effectiveness: Harris Hip Score (HHS)
- Effectiveness: Devane classification

Note: Since patients with no complaints requiring an orthopedic opinion do not usually present for a 2-year visit, only the functional questions of the 2-year HHS score will be collected during the telephone interview.

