## **5. STUDY FEASABILITY**

The clinical research associate (CRA) delegated by the sponsor will make two or three visits to the investigational center:

- An inclusion visit to confirm the investigator's adherence to the protocol and to define the procedures for extracting and transferring anonymized data from the electronic patient record management system. As this is a single-center study, this visit will take place before the protocol is submitted to the CNIL.
- A visit to extract and transfer anonymized data from patient files, and to call patients to obtain their two-year follow-up data. On this occasion, patients will be informed that they may object to the inclusion of their information in this study. During this visit, the sponsor's clinical research associate will check that the data are consistent with the contents of the patient files. He/she will confirm the completeness of the cohort, with consecutive placement of dual-mobility acetabular implants. An anonymized list of all THA during the recruitment period will be obtained and checked to establish the sampling frame. This visit will take place at the start of the study.
- An additional visit by the CRA, to obtain missing data and resolve discrepancies, will take place if necessary.

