## **6. RÉALISATION PRATIQUE DU PROTOCOLE.**

### **6.1. DÉROULEMENT DES VISITES LIÉES A L'ÉTUDE**

The clinical research associate (CRA) delegated by the sponsor will make two or three visits to the investigational center:

- An inclusion visit to confirm the investigator's adherence to the protocol and to define the procedures for extracting and transferring anonymized data from the electronic patient record management system. As this is a single-center study, this visit will take place before the protocol is submitted to the CNIL.
- A visit to extract and transfer anonymized data from patient files, and to call patients to obtain their two-year follow-up data. On this occasion, patients will be informed that they may object to the inclusion of their information in this study. During this visit, the sponsor's clinical research associate will check that the data are consistent with the contents of the patient files. He/she will confirm the completeness of the cohort, with consecutive placement of dual-mobility acetabular implants. An anonymized list of all THA during the recruitment period will be obtained and checked to establish the sampling frame. This visit will take place at the start of the study.

- An additional visit by the CRA, to obtain missing data and resolve discrepancies, will take place if necessary.

In the event of death reported by the patient's entourage without a date, the surgeon will question the civil registry of the patient's commune of birth to obtain the date and cause of death.

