# **7. ELIGIBILITY CRITERIA**

## **7.1. INCLUSION CRITERIA**

Any patient operated by [name] who has undergone hip replacement surgery with SYMBOL CUP DMR HA or SYMBOL CUP CEM acetabular implant and having reach 2-year follow-up on March 01, 2018.

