**2176595 v 0**

du 25 avril 2018

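### Function scores collected by telephone at study start are tested as 2-year results, although those calls come at least 2.15 years after surgery and no time window is set

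*Combined protocol and SAP*

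**What the plan says.** The timing of the 2-year function data has to be pieced together from several places in the combined protocol and SAP.

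- **Source of the score.** The note in section 3.4 explains that patients without complaints do not usually attend at 2 years, so "only the functional questions of the 2-year HHS score will be collected during the telephone interview". Section 1 (research process) makes the telephone interview a fallback for when the medical file is incomplete, covering data up to the 2-year point.
- **When the calls are made.** Sections 5 and 6.1 have the clinical research associate visit to extract the file data and "to call patients to obtain their two-year follow-up data". Section 6.1 adds: "This visit will take place at the start of the study".
- **When the study starts.** The timetable in section 1 reads "Start of the study: As soon as CNIL receipt is received". The receipt in Annex 4 is dated "du 25 avril 2018".
- **Who is eligible.** Section 7.1 takes patients "having reach 2-year follow-up on March 01, 2018". Section 2.2 says the implants have been on the market "since the EC declaration of conformity of April 09, 2014".
- **How the data are used.** Sections 1 and 10.2 plan tests of preoperative against 1-year and 2-year efficacy scores, two-sided at 5%. Section 1 lists HHS, Devane and Charnley as the effectiveness endpoints, and Annex 2 collects all three in its 2-year block. The only assessment date in that block is the date of the telephone interview.

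No section sets a window around 2 years, uses the time from surgery to interview in the analysis, or says which moment the patient is asked to describe.

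**The concern.** A revision or a death has a date, so information gathered late can still be cut at 2 years. Functional status cannot. A patient telephoned at study start gives one of two things: function on the day of the call, which is later than 2 years, or a recollection of function at an anniversary already past. The plan does not say which, and it tests either one under the 2-year label.

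The later date also changes who can answer and about what. A patient who dies between the 2-year date and the call has no telephone score. A patient whose implant is removed in that interval describes a hip that no longer holds the study cup.

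Section 2.2 says the results will support CE mark renewal and a reimbursement application, and calls the study the first clinical evaluation specific to these products. Readers in both settings would take a 2-year HHS at face value.

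**Working it through.** The plan states no interval of its own, so there is no figure to reproduce. The check uses calendar dates only.

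**Inputs**
- Call date: 25 April 2018 (Annex 4 receipt, with study start tied to it in section 1 and calls tied to study start in sections 5 and 6.1).
- Latest eligible surgery: 1 March 2016, which is two years before the 1 March 2018 cut-off in section 7.1.
- Earliest possible surgery: 9 April 2014, the EC declaration in section 2.2. This is an outer limit, because the documents do not date the surgeon's first case.

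**Formulas**
- Interval in days = call date − surgery date; interval in years = days / 365.25.
- Lag in days = call date − second anniversary of surgery.

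**Most recent eligible patient**
- 25 April 2018 − 1 March 2016 = 785 days; 785 / 365.25 = 2.15 years.
- Lag: 25 April 2018 − 1 March 2018 = 55 days.

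**Earliest conceivable patient**
- 25 April 2018 − 9 April 2014 = 1,477 days; 1,477 / 365.25 = 4.04 years.
- Lag: 25 April 2018 − 9 April 2016 = 746 days.

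**Sensitivity of the upper limit to the unknown first case (assumed dates)**

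| Assumed first surgery | Days to 25 April 2018 | Years |
|---|---|---|
| 9 April 2014 | 1,477 | 4.04 |
| 1 July 2014 | 1,394 | 3.82 |
| 31 December 2014 | 1,211 | 3.32 |
| 1 July 2015 | 1,029 | 2.82 |

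**Sensitivity to the call date.** Section 1 expects the report within 30 days of study start. If calls ran to 25 May 2018, the limits become 815 / 365.25 = 2.23 years and 1,507 / 365.25 = 4.13 years.

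The lower limit does not depend on the first case: any call made at the study-start visit is at least 55 days past that patient's 2-year date. If the score is instead recalled function at 2 years, the same lags give the recall period, from about 2 months to at most about 24 months.

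**The case against.** The strongest reply is that few patients may be affected. Section 1 makes the call a fallback, section 4 says the choice of surgeon rested partly on a standard 2-year file record, and section 6.2 describes telephone follow-up as routine. A date-of-interview field would also fit calls made earlier in ordinary care. Section 1 names 2 years as the target, and section 2.2 and the investigator contract already speak of a 2-year minimum. Surgery and interview dates are both collected, the endpoint is secondary, and section 2.3 declares the study descriptive. For the most recent patients a lag of 55 days is small.

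Much of this stands. Patients with a dated 2-year record or an earlier routine call are not affected, and the documents do not give their share. The reply does not remove the point, though. Section 3.4 expects patients without complaints to lack a 2-year visit, section 9 has 2-year data typed straight into the spreadsheet, and Annex 2 has no field showing whether a score came from the file or a call. Collecting the dates makes a remedy possible, but no planned analysis uses them. A descriptive estimate also needs the right time label.

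A reader might be tempted further in three ways that the documents do not support:
- **Taking 2.15 to 4.04 years as the observed spread.** The upper figure needs an operation on the day of the EC declaration, and nothing shows that one took place.
- **Estimating the spread from the national sales tables** (Table 3, "SYMBOL CUP DMR HA: Sales volume in France under this brand", and Table 4). National sales are not one surgeon's operation dates, least of all in a cohort whose stated minimum is 20.
- **Concluding that the 2-year scores are biased in a known direction.** Nothing in the documents gives the sign or size of any change in HHS after 2 years.

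**Conclusion.** The point holds for patients whose 2-year function is obtained by telephone at the study-start visit. On the documents' own dates, a call on 25 April 2018 is at least 785 days (2.15 years) after surgery and at most 1,477 days (4.04 years), the latter as an outer limit only. The plan tests the resulting HHS, Devane and Charnley data as 2-year scores, with no window and no statement of whether present or recalled function is meant. Followed as written, it mislabels the time point or relies on undeclared recall.

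This rests on three assumptions: the calls are made at the visit described in sections 5 and 6.1, that visit is no earlier than the receipt date, and no cup was implanted before the EC declaration. The number of patients affected and the effect in HHS points cannot be derived from the documents.

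A reader might infer that the primary result is also compromised. It is not: revisions have their own date in Annex 2 and section 6.1 provides for tracing undated deaths, so survival can be cut at 2 years. The preoperative versus 1-year comparison is also unaffected. The point should be fixed because the correction is cheap and the results are meant for regulatory and reimbursement use. It does not threaten the study's main conclusion.

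**What to change.** 1. In sections 3.4 and 10.2, state whether the interview asks about function on the day of the call or function at 2 years.
2. If it is present function, label the score 'latest follow-up, minimum 2 years' and report the median and range of the surgery-to-interview interval.
3. Reserve the 2-year label for assessments dated within a window fixed before analysis.
4. Add to Annex 2 the source (file or call) and date of the 2-year assessment.
5. Report how many patients died, and how many had the implant removed, between the 2-year date and the call.

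Two minor clarifications can be made at the same time. Use the same functional subtotal at each visit whenever the comparison involves 2 years, because the 2-year block has no mobility or deformity items and so no total HHS. Reconcile section 3.4, which limits the interview to functional questions, with Annex 2, which also lists pain at 2 years.

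The cost is a few sentences and one source-and-date variable. The interval comes from two dates already in Annex 2, and no extra visits or calls are needed. The real downside is that few or none of the study-start calls may qualify for a strict 2-year label, so the 2-year comparison may shrink or give way to one at latest follow-up.

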### **10.2. DATA ANALYSIS – GENERAL INFORMATION: DESCRIPTIVE APPROACH**

- Descriptive statistics: preoperative, operative, postoperative
- Tabulation of adverse events
- Kaplan-Meier analysis of implant survival
- Comparison tests of preoperative versus 1-year and 2-year postoperative efficacy scores.

Tests will be performed with a two-side alpha risk of 5%. Confidence intervals will be at 95%.

Continuous variables will be tested using Student's t-test. Categorical variables will be tested using Chi-2 test.

No subgroup analysis is planned.

No interim analysis is justified given the strict retrospective nature of the study.

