### **10.4. SECONDARY ANALYSES**

Subgroup analyses: Not applicable

- Descriptive statistics
- Continuous variables: Student's t-test or non-parametric tests in case of a breach of the conditions for applying parametric tests.
- Categorial variables: Chi-2 test.

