### **10.6. METHOD FOR TAKING INTO ACCOUNT MISSING, UNUSED OR INVALID DATA**

As the statistical analysis is descriptive, it will be carried out « *per protocol* » and missing data will not be substituted by values derived from hypotheses.

Visibly aberrant data that the investigator cannot obtain through the usual telephone follow-up will be excluded from the analysis.

Adverse event or follow-up dates for which the day is missing will be substituted by the mid-month date.

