**Annex 2: List of study variables**
**DATA FROM THE COHORT SYMBOL CUP DMR HA AND SYMBOL CUP DM CEM**

PREOPERATIVE DEMOGRAPHICS	Order number of the surgery with this type of implant
	Type of implant DMR HA or CEM
	Month/year of birth
	Sex
	Surgeon identification
	Date of preoperative visit
	Height (cm)
	Weight (Kg)
	BMI
	BMI class
	Operated side
	Etiology / diagnosis
	Medication
	Medication - Specify
	Medical history
	Medical history - Specify
	Local surgical history on the affected hip
	Local surgical history on the affected hip - Specify
	Surgeon's comments
PREOPERATIVE DEVANE & CHARNLEY CLASSIFICATIONS	DEVANE
	CHARNLEY
HHS PAIN	Pain
HHS FUNCTIONAL ABILITIES - WALKING	Lameness
	Support
	Walking perimeter
HHS FUNCTIONAL ABILITIES – DAILY LIFE	Socks and shoes
	Stairs
	Sitting position
	Public transport
HHS – MOBILITY	Flexion °
	Extension °
	Abduction °
	Adduction °
	External rotation °

	Internal rotation °
	TOTAL MOBILITY
DEFORMATIONS	LLI (cm)
	Flessum °
	Adductum °
	Internal rotation °
	TOTAL DEFORMATIONS
	TOTAL PREOPERATIVE HHS
SURGICAL INTERVENTION	Date of surgery
	Age at surgery
	Intervention duration (min)
	Surgical approach
	Type of intervention
	Surgeon's comments
	Operative adverse events
ACETABULAR COMPONENTS	Cup walls
	Fragile acetabulum zone
	Cup identification
	Size
	Cement
	Reaming diameter
	Liner
	Femoral head
	Diameter
	Bone graft
	Screw
	Pegs
	Associated surgical procedure
FEMORAL STEM	Stem identification
	Cement
	CCD angle
	Collar
	Broach size
	Stem size
	Neck length
	Bone graft
STABILITY	Stability of the hip
INCIDENTS	Operative adverse events
SURGEON'S COMMENTS – END OF SURGERY	Surgeon's comments
1-year postoperative assessment	Date
	Death

	Reason for death
1-year postoperative assessment	
DEVANE & CHARNLEY	DEVANE
CLASSIFICATIONS	CHARNLEY
HHS PAIN	Pain
HHS FUNCTIONAL ABILITIES - WALKING	Lameness
	Support
	Walking perimeter
HHS FUNCTIONAL ABILITIES – DAILY LIFE	Socks and shoes
	Stairs
	Sitting position
	Public transport
HHS – MOBILITY	Flexion °
	Extension °
	Abduction °
	Adduction °
	External rotation °
	Internal rotation °
	TOTAL MOBILITY
DEFORMATIONS	LLI (cm)
	Flessum °
	Adductum °
	Internal rotation °
	TOTAL DEFORMATIONS
	TOTAL 1-YEAR FU HHS
Adverse events and reason	Adverse events at 1-year FU
	Date of occurrence of the adverse event
	Potential reason
Treatment	Without revision surgery
	Surgical revision without component revision
	Surgical revision with revision of components
	Date of revision surgery
	Adverse event solved Yes/No

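### Can the Harris Hip Score be compared between the preoperative and 2-year times when Annex 2 lists no HHS sum at both?

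*Combined protocol and SAP*

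**What the plan says.** HHS is a secondary effectiveness endpoint (Summary; section 3.4). A note in section 3.4 explains that patients without complaints do not usually attend at 2 years, and that for this reason "only the functional questions of the 2-year HHS score will be collected during the telephone interview".

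Section 10.2 lists "Comparison tests of preoperative versus 1-year and 2-year postoperative efficacy scores" among the planned analyses. For continuous variables, section 10.4 names Student's t-test, or "non-parametric tests in case of a breach of the conditions for applying parametric tests". Neither section says whether the HHS quantity is the overall score or a part of it. Section 10.6 adds that "missing data will not be substituted by values derived from hypotheses".

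Annex 2 lists the fields. Before surgery there are three HHS sums: "TOTAL MOBILITY", "TOTAL DEFORMATIONS" and "TOTAL PREOPERATIVE HHS". The 1-year assessment repeats the first two and has its own overall score, "TOTAL 1-YEAR FU HHS". The 2-year assessment has a single sum, the functional abilities total. It also carries a pain field under a separate heading.

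**The concern.** The plan promises a test between two times, yet the listed sums at those times are different quantities. Before surgery the most prominent HHS field is the overall total, and at 2 years the only sum is a functional subtotal. The domains that have a preoperative subtotal (mobility, deformations) are not measured at 2 years, while function, the one domain summed at 2 years, has no preoperative subtotal.

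If the two listed sums were subtracted, the preoperative figure would contain pain, mobility and deformation points that have no counterpart at 2 years, and the apparent improvement would be too small. The content of the 2-year HHS also looks unsettled, because section 3.4 speaks of functional questions only while Annex 2 lists pain at 2 years.

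**Working it through.** The documents give no figure to reproduce here. The check is a count of the Annex 2 fields by time point.

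**Sums.**

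| Kind of HHS sum | Preoperative | 1 year | 2 years |
|---|---|---|---|
| Overall | listed | listed | – |
| Mobility | listed | listed | – |
| Deformations | listed | listed | – |
| Functional | – | – | listed |

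That is 3 + 3 + 1 = 7 fields of four kinds. Kinds shared by the preoperative and 1-year times: 3. Kinds shared by the preoperative and 2-year times: 0. The count of kinds is the one that matters. The seven fields are already tied to a time point, so no single field could appear at two times.

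**Items.** Taking membership of the overall total from the Annex 2 headings (an inference, since no scoring rule is given):

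- Preoperative and 1 year: pain 1 + walking 3 + daily life 4 + mobility 6 + deformations 4 = 18.
- 2-year functional total: walking 3 + daily life 4 = 7. These are lameness, support, walking perimeter, socks and shoes, stairs, sitting position and public transport.
- In the overall total but not in the 2-year total: 18 − 7 = 11 (pain 1, mobility 6, deformations 4).
- Recorded both preoperatively and at 2 years: 7 functional items + pain = 8 of 18.

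All 7 functional items are listed preoperatively, at 1 year and at 2 years, so a functional sum can be formed at each time from data already collected.

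**What a mismatch would do.** Let F0 and F2 be the functional sum before surgery and at 2 years, and O0 the preoperative points from the 11 other items. Subtracting the listed sums gives

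F2 − (F0 + O0) = (F2 − F0) − O0.

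When functional change is the target, the result is too low by O0. Provided item scores are not negative, the error understates benefit and cannot create it. O0 has no numerical value here because the documents give no weights; 11 of 18 counts fields, not points.

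**Does the plan lead there?** Nothing in sections 10.2 or 10.4 pairs the 2-year functional sum with the preoperative total. A 2-year overall score is not available: Annex 2 has no 2-year mobility or deformation fields, and section 10.6 would not allow them to be filled in. The sum that the plan itself provides at 2 years is the functional one, and its like-for-like partner is the same 7 items before surgery. The test and its non-parametric fallback apply to that sum as written.

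**Pain.** The reason given in section 3.4 is that patients do not come in. That explains why examined findings are absent, but pain can be asked by telephone. Functional questions there may simply be loose wording for what can be asked without an examination. In Annex 2 the 2-year pain field stands under its own heading, apart from the walking and daily-life items, so the labelled functional total does not depend on it.

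**The case for a change.** The best case for a change is that it would be cheap. Two sentences and one derived subtotal at two times would remove the ambiguity, and the results are intended for CE renewal and a reimbursement application (end of section 2.2). Leaving the HHS quantity unnamed allows it to be chosen after the data are seen, and the pain wording leaves room for 7 or 8 items.

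Part of this stands. The quantity is unnamed, and section 3.4 and Annex 2 do not match on pain. But the room for choice is small. The overall score is unavailable at 2 years, so the candidates are the 7-item sum, which carries the label in Annex 2, and an 8-item sum with pain. If pain was collected as Annex 2 lists it, both are recorded preoperatively and at 2 years, so either gives a like-for-like comparison without the deficit O0. Annex 2 is a list of variables to extract, not of contrasts to test, so the absence of a derived field from it does not show that the derivation was ruled out.

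**Conclusion.** The gap is real, but it is one that analysts fill sensibly, and no change to the plan follows. None of the four kinds of HHS sum is listed both before surgery and at 2 years, yet the 7 items needed for a matched functional sum are collected at all three times and no data are lost. Harm would require subtracting two fields with plainly different labels, against the restriction stated in section 3.4, and the result would understate benefit.

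The reach is one comparison on one secondary endpoint. Implant survival, the preoperative versus 1-year HHS comparison, and the Devane and Charnley classifications (both listed before surgery and at 2 years) are unaffected. The pain discrepancy reads as loose wording and does not alter the 7-item sum.

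This rests on three assumptions: item membership follows the Annex 2 headings, item scores are not negative, and the analyst compares like with like.
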